Number of Injections	2	3	4																						

Injections will be diagonally (45 °) to the skin surface and towards the center of the nodule and the distance between injections in a nodule will be 1 cm (see picture below).

The 2nd cohort will be comprised of subjects with lipedema with substantial fat above the knee. The first 3 subjects will receive 30 mg RZL-012 in 6 injections (0.1mL each) in one leg followed by 30mg RZL-012 (6 injections, 0.1mL each) in the second leg adding up to 12 injections of 60mg RZL-012 (1/4.688th the NOAEL based on HED from GLP toxicology study). The last 3 subjects will receive 40mg RZL-012 in 8 injections (0.1mL each) in one leg followed by 40mg RZL-012 (8 injections, 0.1mL each) in the second leg adding up to 16 injections of 80mg RZL-012 (1/3.125th the NOAEL based on HED from GLP toxicology study).

Cohort 2		
Number of Subjects – Active	3	3
Total Dose RZL-012 (mg)	60	80
Dose per NOAEL*	1/4.688	1/3.125
Number of Injections	12	16

* based on HED from GLP toxicology study

A grid line will be drawn with a makeup pencil in a horizontal plane (Figure 2) 4-6 cm from the suprapatellar fat and its distance from the floor recorded. An attempt should be made to find palpable nodules along the grid line. The injection sites will be marked in circles with a non-erasable pen. This mark should be intensified upon following visits. Injections will be given in multiple sites (4-8 in each leg), diagonally (45 °) to palpable nodules, in the fat above the knee. An attempt should be made to lift the nodule and inject into the middle of the fat-mass. If no nodules are noted in the horizontal plane, drug will be injected in to the fatty tissue (in this case small nodules seen in ultrasound will be followed for changes). Injections will be on the same horizontal plane.

	
Injections will be spread as much as possible and the distance between injected sites will be at least 2-3 cm, according to the number of injections (see picture below).
  
12 injections of RZL-012 16 injections of RZL-012

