3.2. DOSE RATIONALE

The initial dose was determined by the NOAEL established by the Good Laboratory Practice (GLP) extended single dose toxicology study and by the previous phase 0 clinical trial in which 20mg RZL-012 was the highest dose achieved. This initial study is an escalating dose study. If no more than 1 subject experiences intolerable side effects within 14 days following the injection of the last dosed group, according to schedule, an additional cohort of volunteers will be administrated the next dose level.

Cohort 1- will be comprised of subjects with Dercum's disease. All subjects will be injected with RZL-012. Dosing will be calculated according to the size of the nodule (diameter) as determined by ultrasound: 5mg/cm² reaching a maximal dose of 40 mg RZL-012 per subject (1/6.25 the NOAEL based on the Human Dose Equivalent [HED] GLP Toxicology studies).

Cohort 2 - will be comprised of subjects with lipedema with substantial fat above the knee and will be conducted in a dose escalation manner.

The first 3 subjects will receive 60mg RZL-012 (1/4.688th the NOAEL based on HED from GLP toxicology study).

The last 3 subjects will receive 80mg RZL-012 (1/3.125th the NOAEL based on HED from GLP toxicology study).

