3.3. DOSING

3.3.1. Dosing Regimen

The dosing regimen will be a single dose treatment injection of RZL-012 in multiple sites.

Six subjects in cohort 1, all assigned to the RZL-012 treatment group will be dosed at a maximal dose of 40 mg RZL-012 (approximately 1/6.25th the NOAEL as determined in the GLP toxicology study). Dosing will be calculated according to the size of the nodule (diameter) as determined by ultrasound in a dose of 5mg/cm²:

Nodule of 2-2.9cm diameter, as determined by ultrasound, will be injected 2 injections (0.1 mL each, 1 cm apart); total of 10 mg RZL-012.

Nodules of 3-3.9cm diameter, as determined by ultrasound, will be injected 3 injections (0.1 mL each, 1 cm apart); total of 15 mg RZL-012.

Nodules of 4-8cm diameter, as determined by ultrasound, will be injected 4 injections (0.1 mL each, 1 cm apart); total of 20 mg RZL-012.

Cohort 1 – Dercum's disease			
Number of Subjects – Active	6		
Nodule size – diameter (cm)	2-2.9	3-3.9	4-8
Total Dose of RZL-012 (mg)	10	15	20
Dose per NOAEL*	1/25 th	1/18.75 th	1/12.5 th
Number of Injections	2	3	4

Six subjects in cohort 2, all assigned to the RZL-012 treatment group, will be dosed as follows:

The first 3 subjects will receive 30mg RZL-012 in 6 injections (0.1mL each) in one leg followed by 30mg RZL-012 (6 injections, 0.1mL each) in the second leg adding up to 12 injections of 60mg RZL-012 (1/4.688th the NOAEL based on HED from GLP toxicology study).

The last 3 subjects will receive 40mg RZL-012 in 8 injections (0.1mL each) in one leg followed by 40mg RZL-012 (8 injections, 0.1mL each) in the second leg adding up to 16 injections of 80mg RZL-012 (1/3.125th the NOAEL based on HED from GLP toxicology study).

*based on HED from GLP toxicology

Cohort 2 - Lipedema		
Number of Subjects – Active	2	2
Total Dose RZL-012 (mg)	60	80
Dose per NOAEL*	1/4.688	1/3.125
Number of Injections	12	16

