3.3.2. Intolerable Side Effect

An intolerable side effect defined as any of the following treatment-related adverse drug reactions (ADRs):

Any Grade 3 or greater event except for the following (For the following events, a discussion will be held by the PI and the Medical Monitor to decide whether considered as an intolerable side effects):

- Flu-like symptoms and fever that responds to standard treatment within 72 hours
- Localized edema and erythema
- Pruritus
- Pain
- Skin/soft tissue inflammation
- Fat Atrophy
- Liver enzymes abnormality
- Non-significant lab abnormalities, lasting less than 7 days

To establish a threshold for clinical abnormalities and liver enzyme abnormalities the following tables were formed for main expected side effects. For the following abnormalities, associated with the injection site or treatment intolerable side effect would be any Grade 3 or greater event:

Clinical Abnormalities Table

* Erythema – the measured local reaction at the greatest single diameter beyond the injected area surface of all injections (For Dercum's disease – nodules of 2-2.9 cm diameter 2*2 cm, nodules of 3-3.9 cm diameter 3*2 cm nodules of 4-8 cm diameter 4*2 cm. For lipedema -12*2 cm for the first subjects, 15*2cm for the following subjects and 16*2cm for the last subjects), the measurement should be recorded as a continuous variable.

Local Reaction to Injectable Product	Mild (Grade 1)	Moderate (Grade 2)	Severe (Grade 3)	Potentially Life Threatening (Grade 4)
Pain	Does not interfere with activity Repeated use of non-narcotic pain reliever > 24 hours	Interferes with activity	Any use of narcotic pain reliever beyond 7 days following injection or prevents daily activity	Emergency room (ER) visit or hospitalization
Tenderness	Discomfort to touch or with movement	Significant discomfort at rest	Prevents daily activity	ER visit or hospitalization
Erythema/Redness*	2.5 - 7 cm	7.1 - 15 cm	> 15 cm	Necrosis or exfoliative dermatitis
Induration/Swelling**	2.5 - 7 cm and does not interfere with activity	7.1 - 15 cm or interferes with activity	>15 cm or prevents daily activity	Necrosis

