Injections will be spread as much as possible along the grid line and the distance between injected sites (Figure 4) will be:

- At least 3 cm - For subjects receiving 8 and 12 injections.
- At least 2cm - For subjects receiving 16 injections.

Figure 4: RZL-012 Injection Sites in Lipedema Subjects

In lipedema subjects study will be performed in a dose escalation manner:

The first 2 subjects will receive 20mg RZL-012 in 4 injections (0.1mL each) in one leg followed by 20mg RZL-012 (4 injections, 0.1mL each) in the second leg adding up to 8 injections of 40mg RZL-012 ($1/6.25^{\text{th}}$ the NOAEL based on HED from GLP toxicology study).

The next 2 subjects will receive 30mg RZL-012 in 6 injections (0.1mL each) in one leg followed by 30mg RZL-012 (6 injections, 0.1mL each) in the second leg adding up to 12 injections of 60mg RZL-012 ($1/4.688^{\text{th}}$ the NOAEL based on HED from GLP toxicology study).

The last 2 subjects will receive 40mg RZL-012 in 8 injections (0.1mL each) in one leg followed by 40mg RZL-012 (8 injections, 0.1mL each) in the second leg adding up to 16 injections of 80mg RZL-012 ($1/3.125^{\text{th}}$ the NOAEL based on HED from GLP toxicology study).

Within each cohort, dosing of the subjects will progress consecutively from one individual to the other with a minimum of 7-days between subjects to assess safety. This study design will allow the physicians to monitor safety for at least 7 days prior to dosing the next subject. For cohort 2 the decision to proceed to the next dose level will be made after reviewing all safety data collected by Day 14 within 2 ± 1 d of the last dosed subject. The trial will proceed within a cohort provided that no more than one subject experiences intolerable side effects in a cohort, and based on the decision made by the PI and the Medical Monitor.

Each RZL-012 kit contains 1 vial (250 mg/5 mL) corresponding to the number of subjects receiving treatment in each cohort.

RZL-012 will be injected on baseline study visit.

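### Lipedema cohort dosing conflicts: Protocol 6.2.3.1 gives 40/60/80 mg in 2+2+2 subjects, the other dosing sections and the SAP give 60/80 mg in 3+3

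*Protocol*

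**What the plan says.** Protocol 6.2.3.1 describes a three-level escalation in cohort 2. It begins "The first 2 subjects will receive 20mg RZL-012 in 4 injections (0.1mL each) in one leg", repeated in the second leg for 8 injections and 40 mg. The next two subjects get 12 injections (60 mg) and the last two get 16 (80 mg). The same section sets an injection spacing for subjects given 8 injections.

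The other dosing sections describe two levels:

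- Protocol 3.2: "The first 3 subjects will receive 60mg RZL-012 (1/4.688th the NOAEL based on HED from GLP toxicology study"; the last three receive 80 mg.
- Protocol 3.3.1, text: "The first 3 subjects will receive 30mg RZL-012 in 6 injections (0.1mL each) in one leg", doubled over two legs to 60 mg; the last three receive 80 mg.
- Synopsis, cohort 2 table: "Number of Subjects – Active 3 3", under 60 and 80 mg.
- Protocol 8.4.2 (syringe filling): 12 syringes for each of the first three subjects, 16 for each of the last three.
- SAP 5.2.4, 5.2.5, 5.4.1.3 and 5.4.1.4: 60 mg for three subjects, then 80 mg for three.

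Three places fit neither scheme cleanly or carry traces of a third level:

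- The cohort 2 table in 3.3.1 reads "Number of Subjects – Active 2 2", beneath text that assigns six subjects.
- The synopsis and 6.2.3.1 both say "Injections will be given in multiple sites (4-8 in each leg"; four per leg occurs only at 40 mg.
- The erythema and induration footnotes in 3.3.2 set the injected area for lipedema as "12*2 cm for the first subjects, 15*2cm for the following subjects and 16*2cm for the last subjects", which names three groups.

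**The concern.** This is a safety trial, and cohort 2 is its dose escalation. Whichever section the site follows decides the starting dose, the dose of three of the six subjects and how many times safety is reviewed before the dose rises. The conflicting text sits in the treatment procedure, and the opposite instruction sits in the syringe-filling section, so both would be in use on the day of injection.

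The documents do not settle it. SAP 5.8.6 gives the SAP precedence only over data handling and analysis. Protocol 7.5 forbids deviation without written approval, yet following either schedule departs from the other.

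Results are also to be shown by cohort and dose (Protocol 10.5.1, SAP 5.8.2), so the planned layout of those tables depends on the scheme. The point is the contradiction; neither scheme is criticised as a design.

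**Working it through.** **Dose per injection.** Protocol 8.2 gives 250 mg in 5 mL, so 250/5 = 50 mg/mL, and 0.1 mL × 50 mg/mL = 5 mg.

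**Each schedule on its own terms.** Section 6.2.3.1: 8 × 5 = 40 mg, 12 × 5 = 60 mg, 16 × 5 = 80 mg, in 2 + 2 + 2 = 6 subjects. Other sections: 12 × 5 = 60 mg, 16 × 5 = 80 mg, in 3 + 3 = 6 subjects. Both reproduce their stated doses and the cohort size, so arithmetic cannot show which is intended. The 3.3.1 table does not reproduce: 2 + 2 = 4, against 6 stated.

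**By entry order (mg):**

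| Subject | 1 | 2 | 3 | 4 | 5 | 6 | Total |
|---|---|---|---|---|---|---|---|
| 3+3 | 60 | 60 | 60 | 80 | 80 | 80 | 420 |
| 2+2+2 | 40 | 40 | 60 | 60 | 80 | 80 | 360 |
| Difference | 20 | 20 | 0 | 20 | 0 | 0 | 60 |

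**Starting dose.** The cohort 1 limit in 3.2 is "reaching a maximal dose of 40 mg RZL-012 per subject", and 3.2 gives 20 mg as the highest phase 0 dose. Against cohort 1: 60/40 = 1.5 or 40/40 = 1. Against phase 0: 60/20 = 3 or 40/20 = 2.

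**Escalation reviews.** One under 3+3 (60 to 80 mg); two under 2+2+2 (40 to 60, 60 to 80 mg).

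**Nominal time from first to last dose.** Assume 7 days between subjects within a level, a wait to exactly Day 14 of the last subject at each level, and no time for the review itself. 3+3: 7 + 7 + 14 + 7 + 7 = 42 days. 2+2+2: 7 + 14 + 7 + 14 + 7 = 49 days. If the Day 14 visit falls a day early within its window, these become 7 + 7 + 13 + 7 + 7 = 41 and 7 + 13 + 7 + 13 + 7 = 47.

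**Tables by dose.** One affected subject shows as 1/3 = 33.3% or 1/2 = 50%.

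**Footnotes in 3.3.2.** Under 3+3 there is no middle group, so the injected area for a 60 mg subject could be read as 12*2 cm (first) or 15*2 cm (following). Six sites on one line at the 3 cm minimum that 6.2.3.1 sets for 12 injections span at least 5 × 3 = 15 cm, which does not fit a 12 cm length.

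**The case against.** The best reply is that 3+3 is plainly intended. The synopsis, 3.2, the 3.3.1 text, 8.4.2 and the SAP agree, and 6.2.3.1 is the outlier. The outlier is also the cautious one: a site following it would never give a subject more than 3+3 allows. Both schemes end at 80 mg, with the same 7-day spacing, Day 14 review and limit of one subject with intolerable side effects per cohort. Escalation needs a decision by the investigator and the Medical Monitor, and there is one listed site, so a mismatch would probably be noticed.

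On the analysis side, the exact interval for the primary endpoint is reported by cohort and overall (Protocol 10.5.4, SAP 5.8.13), so cohort 2 stays at n=6. The analysis is mainly descriptive, no power calculation is disturbed, and administered doses are tabulated and listed.

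Most of this is correct and limits the consequences. The elapsed days are nominal figures. The footnotes describe the area beyond which a reaction is measured and leave the grade cut-offs unchanged; no changed grade has been shown. What the reply does not do is remove a full, current and different regimen from the treatment section. That 3+3 is intended remains an inference, and noticing a conflict on the day does not tell the site which starting dose is authorised.

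**Conclusion.** The inconsistency is real and must be fixed. Three of six lipedema subjects (1, 2 and 4) have two prescribed doses 20 mg apart, the starting dose is 40 or 60 mg, and there are two escalation reviews or one. The 3.3.1 table is separately wrong, showing four subjects for a cohort of six.

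The dose differences follow from the stated concentration and injection counts and need no outside assumption beyond dosing in entry order. The 42 and 49 days rest on the nominal Day 14 wait with review time excluded. The weight of the finding lies in the conflicting dose and escalation rule; the primary analysis is unaffected, and the per-dose tables are a secondary consequence.

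**What to change.** Before cohort 2 is dosed, amend the protocol to one scheme chosen by the sponsor and investigator. The documents do not give dosing status; if cohort 2 has already been dosed, record which scheme was used and correct the text to match.

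- **If 3+3** (the scheme in most sections and the SAP): replace the three-level text in 6.2.3.1, correct the 3.3.1 table to 3 and 3, delete the spacing rule for 8 injections, change the range per leg from 4–8 to 6–8 in the synopsis and 6.2.3.1, and give one injected area for each of the two doses in both 3.3.2 footnotes.
- **If 2+2+2**: change the synopsis, 3.2, the 3.3.1 text and table, 8.4.2, and SAP 5.2 and 5.4, and tie the three footnote areas to 40, 60 and 80 mg.

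The cost is one protocol amendment; the SAP changes only under 2+2+2. Neither choice adds patients. Compared with 3+3, 2+2+2 carries one more Day 14 review and, at the nominal timing, 7 more days of cohort 2 dosing.

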6.2.4. Baseline Visit

Baseline visit is defined in the study as Day 0. Baseline visit will be performed to complete screening evaluation, and to review all procedures necessary to confirm subject eligibility. Subjects will stay under supervision in the study center till 8h + 3h following drug injection.

Screening information may be considered for baseline data if acquired within the adequate timeframe as described in Table 2.

Table 2: Subject Information and Timeframes

Information	Timeframe	Follow-up Timeframe
Informed Consent Form	Signed prior to any study dedicated procedure	
Medical History and Concomitant Medications	At Screening Day visit	
Physical examination	At Screening Day visit and at Day 28	
Pain Measurement	At Screening Day visit and at Days 14, 28	At Day 56
QOL Measurement in lipedema subjects	At Screening Day visit and at Days 14, 28	At Day 56
Vital Signs	At Screening Day visit and at Days 0 (pre and following injection), 1, 7, 14, 21, 28	
Pulse rate	At Day 0 (following injection) and at Day 1	
ECG	At screening Day 1 visit, at Day 0 (following injection) and at Days 1, 14, 28	
Draize Score at the Injected Site	At Screening Day and at Days 0 (pre- and following injection), 1, 7, 14, 21, 28	At Day 56
Serology assays (HbSAg, HCV and HIV)	At Screening Day visit	
Drug screen	At Screening Day visit	
Serum chemistry and Hematology	At Screening Day and at Day 1, 3, 7, 14 and 28	
Urinalysis	At Screening Day visit and at Days 14 and 28	

Information	Timeframe	Follow-up Timeframe
Ultrasound for nodules quality and size. Fat thickness – for lipedema	At Screening Day visit and at Day 28	At Day 56
Ultrasound for nodules size and selection for injection	At Days 0 (pre- injection)	
Photography of the Injected Sites	At Screening Day visit and at Days 1, 7, 14, 21, 28	At Day 56
AE Assessment	At Days 1, 3, 7, 14, 21, 28	At Day 56

6.2.5. Subject Site Visits

Subject site visits will be performed \pm 1 day from scheduled date. All data relevant for the visit needs to be obtained within 3 days (e.g., blood tests) of visit.

Subject sites visits will include procedures as described in Appendix I.

For site visit that results in study discontinuation, see termination visit in Section 6.2.6.

6.2.6. Termination Visit

Once study is discontinued, all reasonable measures should be taken to perform a termination visit. Termination visit should include all procedures necessary to complete subjects' records: AE reporting, any clinical laboratory test needed to evaluate unresolved AEs, evaluation of response, recovery of all clinical supplies and compliance diaries, and updating of subject contact information. An effort should be made to perform all activities conducted on visit Day 28.

6.2.7. Unscheduled Visit

Unscheduled visits will be performed upon investigator's discretion, upon Sponsor request to redo tests with unusual results or complete missing results and may occur upon subject's decision with no notification in advance. Unscheduled visits will include any study procedure deemed necessary, as described in Section 6.1.

7. SAFETY CONSIDERATIONS AND GUIDANCE FOR INVESTIGATORS

Adherence to protocol monitoring procedures along with the following safety guidance will aid and promote subject safety.

7.1. STUDY RESTRICTIONS REGARDING CONCOMITANT MEDICATIONS

Subjects may not receive the following medications while on study:

- Chronic treatment with systemic steroids or immunosuppressive drugs.
- Chronic treatment with Non Steroid Anti-Inflammatory Drugs (NSAIDs) and aspirin.
- Any investigational product other than RZL-012.

Before dosing, analgesic gels such as Lidocaine (e.g., Emla) or Pramoxine should be used to numb the injected site. An ice pack may be applied on the site of injection following dosing to help reduce pain. At day 1 following injection application of the anti-histamine Benadryl Gel (Diphenhydramine hydrochloride 1 %for topical use only) should be initiated prophylactically, according to drug instructions for use, to avoid itching at the injected area. Benadryl Gel should be applied for 7 days.

Use of nattokinase is prohibited and the use of other supplements or complementary medicines/botanicals should be approved by the PI, except for conventional multivitamin supplements. The use of prohibited supplements should be stopped a week before injection.

7.2. SAFETY MEASUREMENTS

Simple measures may help avoid specific AEs associated with the use of the RZL-012 investigational product. Thus, study subjects must be informed of possible AEs that occurred in animal studies (rats and pigs):

- Any injection site reaction may occur. Pain, swelling, itching, edema, erythema, hematoma, etc.
- Slight transient injection site bleeding following injection may occur.
- Itching in the injected area may occur, and study subjects should be advised to use an antihistamine gel for topical use according to drug recommendations, wear wide cotton shirts, prevent touch with irritable clothing, avoid scratching and avoid exposure to direct sun. Itching is expected till 7 days following drug injection.
- Local erythema in the injected area.
- Local heat in the injection area.
- Study restrictions regarding concomitant medications are listed in Section 7.1.
- The local subcutaneous fat reduction may appear as a slight dip in the skin surface. This decline may be temporary and transient.

- Transient increase (72%) in the WBC count by 24 hours following injection, which returned to basal level after 14 days. Probably associated with the inflammatory response at the site of injection and involve neutrophils, monocytes and eosinophils.
- Increased level of BUN and of creatinine and minimal single cell necrosis was observed in tubular epithelium at cortico medullary junction of kidney in rats receiving a dose 25 times the highest dose in this study. All abnormalities were found to be reversible by Day 14.
- Increased AST level which is most typical of myofiber injury associated with study related procedures. This elevation was found to be reversible by Day 14.
- Transient increase of serum CRP levels (in rats) which returned to the basic level by 14 days.
- Marked irritancy in the injected subcutaneous tissue resulting in coagulation necrosis of relatively large areas in the subcutaneous tissue planes acutely. Necrosis persisted for up to 14 days and was accompanied by early evidence of healing in the form of chronic inflammation and fibrosis.
- Local inflammation (minimal to moderate) with muscle degeneration, epidermal/dermal necrosis (minimal to severe) and parakeratosis (minimal). Inflammation observed at injection site was also extended to adjacent subcutaneous adipose tissue (SAT). By 56 days the inflammation was minimal, muscle degeneration was not evident and inflammation to adjacent SAT was present.
- A slight elevation in body temperatures was noted in male pigs.
- Sinus tachycardia (in pigs), occurring at the 4 hour interval post dosing.
- In addition, other acceptable treatment to relieve drug-related AE's should be used at Investigator's discretion.

Study subjects must be informed of possible AEs that occurred in clinical studies (phase 0):

- At the injection site -local and transient: erythema, edema, pruritus, anesthesia, pain, mass (subcutaneous scar).
- Abdominal abscess
- Transient moderate to severe elevation of the liver enzymes: ALT and AST.

